For participants completing the urine test, verbal consent will be obtained over the phone, prior to mailing the testing kit. Participants will be contacted within 1-2 business days of completing the 6-month follow-up survey to consent to the urine test and review instructions. The urine test will be offered to all participants who reported smoking abstinence at 6-month follow-up.

Re-consenting of participants regarding the audio recordings will take place by telephone and documented in their study record. This language has been modified in the updated consent document that has been uploaded.

**1.13** Provide a detailed description in sequential order of the study procedures following the consent process - DO NOT cut and paste from the Consent Document.

Describe study populations separately if they will be participating in different procedures

DESCRIBE:

Control populations, if applicable

Any randomization, if applicable

What participants will be asked to do/what happens in the study (in sequential order)

The time period over which procedures will occur

Long-term follow-up and how it occurs

The recruitment and study procedures will occur for about 3 years. Participants will be asked to participate in the study for a total of six months that will include completing the quitline coaching sessions which can take 1-4 months, and follow-up at 3 and 6 months; however, they can withdraw from the study at any time. During this time, half of the participants will also be asked to work with a Navigator to assist with the basic needs from their initial 2-1-1 call.

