All participants who complete the 6-month follow up survey (estimated N=1200) and report smoking abstinence and no use of nicotine replacement products in the past 7 days (estimated <14% = N<168) will be invited to biochemically assess carbon monoxide levels or cotinine levels. If participants are willing to participate, they will be mailed a urine test to measure their cotinine levels, which is a metabolite of nicotine. The urine test, which can be purchased at any local pharmacy over-the-counter, will be mailed to participants with instructions for sending the results. The study team will not receive any biological samples or testing materials in the mail. Instead, participants will be instructed to send a picture of their results to the study email account and/or phone account. The photo will include only the results: a photo of the dipstick next to the results card. No personal identifiable information will be included in the photo. The results will be linked to the participants study ID via their phone number from which the photo was sent. Consent will be obtained prior to sending the testing kit in the mail via phone script (see attached). Results will be recorded in participants study record. Incentives will be mailed to participants after result has been received by study team.

**1.14** Will participants be randomized?

Yes

**1.15** Will any of the following be used to collect information from the participant or others?

Screening questions or screening/eligibility questionnaires

Surveys

Questionnaires

Stimuli

Any other written assessments

Yes

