Helping the Poor Quit Smoking: Specialized Quitlines and Meeting Basic Needs

NCT03194958

3/8/17

Provide a summary of the analysis methods you will use, including, if applicable, the data points or outcomes you will analyze.

Aim 1: For each group, descriptive statistics will show the proportion of baseline participants reached by the quitline, number of quitline sessions completed, and additional services (Print, Text2Quit, WebCoach) used. Differences by group will be compared using chi-square tests or logistic regression for categorical variables and by t-tests, linear regression or appropriate non-parametric tests for continuous variables. Secondary analyses will explore any differences by covariates such as gender, age, rural/urban residence, and unmet basic needs. Significant intervention and/or covariate effects will be included in all further analyses.

Aim 2: We will calculate quit rates for each group by dividing the number of participants who meet this criterion by the number of participants randomized to that group. Analysis will follow intent-to-treat (ITT) principles; all participants who completed a baseline assessment and were randomized will be included in analysis. Those lost-to-follow-up, refusing interviews, or otherwise unreachable will be assumed to be smokers. We will use logistic regression to compute odds ratios and 95% confidence intervals for group differences in quit rates, comparing Standard and Specialized Quitlines with and without a Basic Needs Navigator, with the “standard quitline, no navigator” group as the referent.

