We will conduct analyses of secondary outcomes (7 and 30 day point prevalence abstinence, >24 hour quit attempt, use of pharmacotherapy, participation in cessation counseling) at 3 and 6 month follow up. Consistent with other reports in the literature, we also will compare the results from self-reported smoking cessation to results that adjust for biochemical validation. First, we will consider all participants who fail the biochemical validation and those that did not return a saliva sample to be smokers and recalculate abstinence rates by group. Second, we will recalculate abstinence rates by group, assuming that the true smoking cessation rate of participants who do not complete a follow up survey or do not return their saliva samples is the same rate as for those who did return a sample. Additionally, we will explore differences between people who do and do not agree to receive a kit and do and do not return a saliva sample. Analyses will be repeated with multiple logistic regression to include

potential baseline covariates (e.g., socio-demographics, rural/urban residence, nicotine dependence, readiness to quit). Cases with missing data on covariates will be excluded from analyses.

We also will conduct a series of sensitivity analyses to evaluate the robustness of our findings. To assess effects of protocol deviations, we will compare results of per-protocol analyses to ITT analysis. We will examine quit rate differences by intervention “dose” (i.e., number of completed quitline calls, number of navigator contacts), number of unmet basic needs, demographics, and smoking variables assessed at baseline, and extent of problem resolution at 3- and 6-month follow-up. We will assess the effect of missing data by comparing ITT results to a complete case (all data available at 6-month follow-up) analysis.

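### The second biochemical recalculation, a secondary analysis, gives survey non-completers the confirmation rate of claimed quitters, which does not fit people with no 6-month self-report

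*SAP*

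**What the plan says.** The primary Aim 2 analysis counts every randomized participant and treats missing outcomes as smoking: "Those lost-to-follow-up, refusing interviews, or otherwise unreachable will be assumed to be smokers".

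The SAP then adds a secondary comparison: "we also will compare the results from self-reported smoking cessation to results that adjust for biochemical validation". It has two parts. The first counts failed tests and unreturned samples as smoking. The second recomputes the result for each arm, "assuming that the true smoking cessation rate of participants who do not complete a follow up survey or do not return their saliva samples" equals that of the sample returners. One rate thus serves two different groups: people who did not complete the survey, and people who did not return a sample.

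The SAP does not say who is offered a kit. The protocol does:

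- Protocol 1.12: "The urine test will be offered to all participants who reported smoking abstinence at 6-month follow-up".
- Protocol 1.13, follow-up: "All participants who complete the 6-month follow up survey (estimated N=1200) and report smoking abstinence", with the further condition "no use of nicotine replacement products in the past 7 days (estimated <14% = N<168) will be invited".

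The two protocol sections differ on recent users of nicotine replacement therapy (NRT), but in both only self-reported abstainers are tested.

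**The concern.** For an abstainer who is offered a test and returns nothing, borrowing the returners' rate is a reasonable assumption, because both have made the same claim. A survey non-completer has made no claim. Everyone who can return a result has already reported not smoking, so the returners' rate answers a narrower question: of those who say they quit, how many does the test confirm? Using it for non-completers treats them all as if they had reported abstinence.

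At stake is a prespecified by-group result whose purpose is to show whether the self-report findings survive validation. Run as written, it would report abstinence far above the respondents' own validated rate, and most of the quitters it counts would have given no 6-month self-report. Adding the same large block of imputed quitters to each arm would also pull the odds ratio towards 1, which could be misread as a lack of robustness.

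**Working it through.** **Inputs from the documents.** 2,000 randomized, 500 per group, and at least 60% reached at 6 months (SAP 1.23); 1,200 completers and fewer than 168 (under 14%) eligible for the test (Protocol 1.13).

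**Inputs assumed.** The confirmation rate c is not given. Self-reported smokers are kept as smokers, a step the SAP does not state. The upper figure of 168 stands for all self-reported abstainers.

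**1. The plan's own figures.** 2,000 × 0.60 = 1,200, and 1,200 × 0.14 = 168. Both reproduce. Non-completers: 2,000 − 1,200 = 800, a maximum because 60% is a minimum.

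**2. Overall abstinence.**

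| Treatment of the 800 | Formula | Rate | c = 0.5 | c = 0.8 | c = 1.0 |
|---|---|---|---|---|---|
| Returners' rate (SAP rule) | (168 + 800)c / 2,000 | 0.484c | 24.2% | 38.7% | 48.4% |
| Validated respondent rate | 168c / 1,200 | 0.14c | 7.0% | 11.2% | 14.0% |
| Counted as smokers | 168c / 2,000 | 0.084c | 4.2% | 6.7% | 8.4% |

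The like-for-like ratio is 0.484 / 0.14 = 3.46, and c cancels. The non-completers' share of counted quitters is 800 / 968 = 83%.

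**3. Sensitivity of the ratio.** With f the follow-up proportion and p the respondents' quit rate, the ratio is [(1 − f) + fp] / p.

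- f = 0.6, p = 0.14: 0.484 / 0.14 = 3.5
- f = 0.8, p = 0.14: (0.20 + 0.112) / 0.14 = 2.2
- f = 0.6, p = 0.10: 0.46 / 0.10 = 4.6
- f = 0.6, with an assumed 40 NRT-using abstainers added (208 / 1,200 = 0.173): 0.504 / 0.173 = 2.9

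**4. Group comparison (illustration).** An even split of the SAP's 10% overall quit rate and 5-point difference gives 7.5% vs 12.5% among respondents, OR (0.125 / 0.875) / (0.075 / 0.925) = 1.76. Assume f = 0.6 and c = 0.8 in both arms. Under the SAP rule an arm's rate is c[(1 − f) + fp]:

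- 0.8 × (0.4 + 0.045) = 35.6%
- 0.8 × (0.4 + 0.075) = 38.0%
- OR = (0.380 / 0.620) / (0.356 / 0.644) = 1.11

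For comparison:

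- Validated respondent rate: 6.0% vs 10.0%, OR 1.74.
- Missing counted as smoking: 3.6% vs 6.0%, OR 1.71.

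Under the SAP rule the OR stays between 1.08 and 1.12 for c from 0.3 to 0.9. The absolute difference of 2.4 points equals that under missing = smoker; the OR collapses because of the inflated base.

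**5. Direction with unequal follow-up.** In c[(1 − f) + fp] the coefficient of f is −c(1 − p), so worse follow-up raises an arm's rate. With an assumed 65% vs 55% follow-up and p = 0.14 in both arms, the gap is 0.10 × 0.86 × c = 0.086c: 4.3 points at c = 0.5 and 7.7 at c = 0.9, in favour of the arm with more loss.

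**The case against.** The strongest reply is that this is a mismatch between documents rather than a poor analytic choice. The SAP speaks of saliva and never restricts the kit to abstainers; the restriction and the urine test appear only in the protocol. If samples had been meant for respondents generally, the sentence would be a coherent missing-at-random rule. It may also be compressed wording for the validated rate of all respondents, and the sources the SAP cites for it cannot be consulted here. Either explanation is possible. Neither changes the position: the current rule fails under the current testing procedure, and nothing elsewhere corrects it.

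A second reply is that the consequence is small. The primary outcome is self-reported, the first recalculation stands, and a missing-data check is planned: "We will assess the effect of missing data by comparing ITT results to a complete case". A rate near 39% beside a self-reported intention-to-treat rate of 168 / 2,000 = 8.4% would also be conspicuous. This limits the weight of the point. The complete-case check, however, neither uses nor repairs this rule.

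Some stronger readings are tempting but not supported:

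- A reader might infer that self-reported smokers also receive c, so that the overall rate is simply c (80% at c = 0.8). The SAP's wording refers to participants' own samples, which suggests people who were asked for one. That reading is strained.
- A reader might describe the non-completers as never reached. The SAP includes refusers among those with missing outcomes, and a 6-month non-completer may have answered at 3 months.
- A reader might call the rate 5.8 times too high (0.484 / 0.084). That treats missing = smoker as the truth, when it is itself an assumption.
- A reader might expect unequal follow-up or unequal confirmation between arms. The documents predict neither.

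**Conclusion.** The rule is wrong as written, in a secondary analysis only. It applies a confirmation rate among claimed quitters to people who made no claim. At 60% follow-up and 168 abstainers it gives about 3.5 times the abstinence of a like-for-like rule, and about 83% of counted quitters have no 6-month self-report. The ratio does not depend on c, but it does depend on the respondents' quit rate and on follow-up, and it shrinks as follow-up improves. These figures rest on keeping self-reported smokers as smokers and on taking 168 as all abstainers.

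The fall in the odds ratio from 1.76 to about 1.11 is an illustration. It assumes c = 0.8, equal follow-up in both arms and an even split of the planning quit rate. A reader might infer that the trial's main conclusion is at risk; it is not, because the primary intention-to-treat analysis and the first recalculation do not use this rule. The correction should still be made before analysis, because the result is prespecified, reported by group and meant to be set beside the self-report findings.

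**What to change.** In the second recalculation, state:

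1. Each arm's confirmation rate applies only to self-reported abstainers who were offered a test and returned no result.
2. Self-reported smokers stay smokers.
3. Survey non-respondents receive their arm's validated rate among all 6-month respondents, that is, the self-reported abstinence rate times the confirmation rate.

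Item 3 is one coherent choice among several, and its point estimate equals a validated complete-case rate. It is preferred here because missing = smoker is already covered by the first recalculation. Whichever rate is chosen, the SAP must name it.

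To make this workable, reconcile Protocol 1.12 and 1.13 on whether abstainers using NRT are offered the test, since this decides who counts as a non-returner, and say how abstainers not offered a test are counted. Align the SAP's saliva wording with the protocol's urine test. The cost is a few SAP sentences and the reconciliation of two protocol statements, with no new data.

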Use THIRD person active voice. For example, "the principal investigator will identify potential participants, the study coordinator will discuss the study with participants over the telephone and schedule the first study visit, etc..."

Describe the steps that will be taken by the research team to minimize the possibility of coercion or undue influence during the consent process

The study population will come from United Way 2-1-1 callers that are Missouri residents who are 18 years and older, have self-identified as smokers. United Way 2-1-1 is not engaged in research activity. United Way 2-1-1 Missouri Information Specialists will identify callers that are English-speaking, not experiencing crisis, 18 years and older, and are cognitively capable of understanding the process and what is being asked. Once callers have been screened by the 2-1-1 Information Specialists using the provided recruitment telephone script, express interest in the study, they will be considered to be interested and potential study participants by 2-1-1. Their contact information will be recorded in a spreadsheet and electronically retrieved by the Washington University (WUSTL) Research team at the close of the recruitment period (end of the business day Monday-Friday over the three year recruitment period). United Way 2-1-1 will NOT do any consenting. They will only invite callers to participate in the research project. When the spreadsheet is received, the participants' information will be entered into a secure database. After which, participants will be contacted by the WUSTL research staff to confirm their interest and eligibility, obtain verbal informed consent, administer the baseline survey, and obtain detailed contact information and preferences. This process will happen in 1-2 business days after the information has been received from United Way 2-1-1. After completing the baseline assessment, participants will be enrolled into quitline services, and wait to be contacted by the quitline (Alere Wellbeing, Inc./Optum) in the next 1-3 business days. During this time, collateral contacts will also be consented to be called during the study if the participants cannot be reached on their primary and secondary numbers provided.

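### The covariate-adjusted quit models drop randomized participants with a missing baseline covariate, against the SAP's own intent-to-treat statement; the effect is probably small and the fix is cheap

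*SAP*

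**What the plan says.** The SAP's Aim 2 text defines the analysis population by intent to treat: "all participants who completed a baseline assessment and were randomized will be included in analysis". Missing outcomes have their own rule: "Those lost-to-follow-up, refusing interviews, or otherwise unreachable will be assumed to be smokers". The group comparison is then a logistic regression with the standard quitline without navigator as referent. That paragraph names no covariates.

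The following paragraph adds a covariate-adjusted pass: "Analyses will be repeated with multiple logistic regression to include" "potential baseline covariates (e.g., socio-demographics, rural/urban residence, nicotine dependence, readiness to quit". The covariates are given as examples, so the list is open. The next sentence is "Cases with missing data on covariates will be excluded from analyses". No imputation, missing category or threshold is stated.

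Two other sentences bear on the point. Among the sensitivity analyses: "We will assess the effect of missing data by comparing ITT results to a complete case (all data available at 6-month follow-up) analysis". At the end of Aim 1: "Significant intervention and/or covariate effects will be included in all further analyses".

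**The concern.** The missing-outcome rule does not cover covariates, so the exclusion sentence amounts to listwise deletion in the adjusted models. A participant whose 6-month smoking status is known can be dropped for one unanswered baseline item, while a participant who was never reached stays in as a smoker. That conflicts with the commitment to include everyone randomized.

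What is at stake is comparability and a little precision. Adjusted and unadjusted odds ratios differ somewhat even in the same people. Deletion adds a second, avoidable source of difference, and a reader who sees the two disagree cannot tell adjustment from a change of sample.

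The Aim 1 carry-forward sentence raises a further question. It makes no exception for the main Aim 2 model. If it applies there, a covariate found significant in Aim 1 would enter that model, and the exclusion sentence could then remove randomized participants from it.

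**Working it through.** **1. Which results does deletion reach?**

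- *Crude quit rates* (quitters divided by number randomized): no covariates, so not affected.
- *Adjusted repeat models*: affected whenever a covariate is missing.
- *Main Aim 2 logistic model*: two readings. The adjusted pass is described as a repeat, which implies an unadjusted first pass that deletion cannot reach. The Aim 1 carry-forward, read literally, puts significant covariates into every later analysis, and then it can. Exposure needs both a significant Aim 1 covariate and missing values on it.
- *Complete-case check*: it selects on data at 6 months, so it does not test the loss from missing baseline covariates.

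**2. How many people?** The documents give no rate of covariate missingness. Assume m = 1% to 3%.

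- Same people miss every item: loss = m × 2,000 = 20 to 60. At the SAP's expected 60% follow-up, 0.60 × 20 to 0.60 × 60 = 12 to 36 of these would have a known outcome, if missingness is unrelated to follow-up.
- Two items (nicotine dependence and readiness to quit) missing independently: loss = 2,000 × [1 − (1 − m)²]. At 1%: 2,000 × 0.0199 = 40. At 3%: 2,000 × 0.0591 = 118. Rural/urban residence is left out because it can probably be derived from the mailing address (Protocol 1.8.a). Age follows from date of birth. Because the covariate list is open, the final count could differ.

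**3. Effect on power (illustration).** SAP Section 1.23 states only that power is sufficient. It gives no power value, alpha or sidedness, so there is no figure to reproduce. Assume a two-sided 5% pooled test of two proportions between the extreme arms, and read the SAP's OR of 1.8 and 10% total quit rate as the average of those two arms. Solving gives p₁ = 7.41% and p₂ = 12.59%, a difference of 5.18 points.

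Power = Φ{[(p₂ − p₁) − 1.96 √(2 p̄(1 − p̄)/n)] / √[(p₁(1 − p₁) + p₂(1 − p₂))/n]}, with p̄ = 10%.

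At n = 300: (0.0518 − 1.96 × 0.02449)/0.02440 = 0.156, so power is 56.2%.

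| n per arm | no loss | 1% loss | 3% loss |
|---|---|---|---|
| 300 (followed-up sample) | 56.2% | 55.8% | 54.9% |
| 500 (all randomized) | 78.0% | 77.6% | 76.8% |

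The first row is closer to the SAP, which gives these rates directly after the total of 1,200 followed up, or about 300 per arm. The second row puts the same rates on 500 per arm. The SAP itself says quit rates would be lower in the intent-to-treat analysis, so this row is illustrative only. In both rows the drop at 3% loss is a little over one percentage point.

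**4. Effect on the odds ratio.** If missingness is unrelated to arm and outcome, the standard deviation of the change in log OR from deleting a fraction d is SE × √[d/(1 − d)]. At 500 per arm SE = 0.2175, so it is 0.0219 at d = 1% and 0.0383 at d = 3%. An OR of 1.80 would move at random within about 1.72-1.88 (1% loss) or 1.67-1.94 (3% loss), in 95% of cases and with no systematic direction.

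**The case against.** The best defence is that little or nothing will be missing. The analysis population has completed a baseline assessment, and Protocol 1.12 has research staff "obtain verbal informed consent, administer the baseline survey, and obtain detailed contact information and preferences" by telephone. Daily smoking and a plan to quit within 30 days are inclusion criteria (Protocol 1.7), so readiness is partly captured at entry. The affected models are also secondary repeats, complete-case adjustment there is conventional and declared in advance, and reporting the number in each model would reveal a change of sample.

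Most of this stands, and it keeps the point minor. It does not remove it. A completed assessment need not have an answer to every item, and the SAP provides an exclusion rule for gaps. Reporting the number shows that the sample changed, but not what the change did to the odds ratio.

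Two stronger readings are tempting. A reader might infer that the primary comparison itself breaks intent to treat. The documents do not establish that: the Aim 2 model names no covariates, and the carry-forward route is conditional and open to interpretation. A reader might also infer a biased treatment effect. Nothing in the documents suggests that baseline missingness would depend on study arm. The opposite inference, that the main model is certainly safe, also goes too far, because the carry-forward sentence does not exempt it.

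**Conclusion.** The inconsistency is in the text and needs no assumption: the SAP promises all randomized participants, then excludes some from the adjusted quit models, and no planned check covers that loss. The crude quit rates are safe. Whether the main Aim 2 logistic model is exposed depends on a sentence that the SAP leaves ambiguous.

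The size is unknown and probably small. Under an assumed 1-3% missingness, the loss is 20-60 people if gaps cluster, or 40-118 if two items are missing independently. The clustered loss costs about one percentage point of power at most rates considered here. These figures rest on the assumed rates and on a two-sided 5% test. The expected harm is to precision and comparability, with no systematic bias in the group contrast. Minor.

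**What to change.** Replace the exclusion sentence with:

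> In the covariate-adjusted intent-to-treat quit models, missing baseline covariates will be filled by simple imputation ignoring study arm (or a missing category for categorical covariates), so that these models include all randomized participants.

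Do not extend this to analyses that restrict the sample by design: per-protocol, complete-case, and the comparisons of people who do and do not accept or return a test kit.

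State also that the main Aim 2 group comparison is unadjusted and exempt from the Aim 1 carry-forward sentence.

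The cost is a few edited SAP sentences, no new data, and slight extra analysis work.

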Follow-up: Follow-up at 3 & 6 months. The primary study outcomes are cessation-related. Participants will be asked if they smoked at all in the past 7 days and past 30 days to assess point prevalence abstinence. Those who report any smoking in the past 7 days will be asked if they quit for at least 24 hours since the previous survey and to report on their nicotine dependence measured by the Heaviness of Smoking Index (cigarettes per day; time elapsed between waking and smoking). These items from the Fagerstrom Test of Nicotine Dependence are reliable over time with good predictive validity. All participants will report use of any pharmacologic cessation aids (i.e., NRT, bupropion, Chantix), self-help, or counseling resources they have used since the prior survey. Successful quitters ( 7 days) will report their confidence in staying quit and all others will report their greatest barriers to cessation (open ended), current motivation (1=very low; 10=very high), and readiness to quit. Follow-up surveys also will assess changes in unmet basic needs (items described in "Baseline") and problem resolution for each reason they called 2-1-1 at enrollment ("When you called 2-1-1 on <date> you asked for help with <problem>. Has that problem been resolved?"). Reactions to the quitline and navigation interventions and staff will be assessed with measures from our previous studies assessing usefulness (e.g., was it helpful?), satisfaction (would you recommend it to others?) user experience (were they easy to talk to?); quit coaches and navigators (similarity, liking, expertise, sincerity, trustworthiness); and intervention appropriateness (relevant to my life and situation, designed for someone like me).

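### Analyses by call count, navigator contacts, per-protocol status and problem resolution are listed as robustness checks, but each depends on behaviour after randomization and cannot test the randomized result

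*SAP*

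**What the plan says.** The last paragraph of the SAP's Aim 2 text opens with its purpose: "We also will conduct a series of sensitivity analyses to evaluate the robustness of our findings". It then lists several comparisons.

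- **Per-protocol:** "To assess effects of protocol deviations, we will compare results of per-protocol analyses to ITT analysis". The per-protocol population is not defined.
- **Dose:** "We will examine quit rate differences by intervention" dose, measured as "number of completed quitline calls, number of navigator contacts".
- **Problem resolution:** quit rates by "extent of problem resolution at 3- and 6-month follow-up".
- **Baseline factors:** unmet needs, demographics and smoking variables. These precede randomization and are not part of this point.
- **Missing data:** a comparison of ITT with complete cases at 6 months, not tied to the dose analyses.

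The only rule for setting a missing outcome in the main analysis is in the SAP's first Aim 2 paragraph, where participants lost, refusing or "otherwise unreachable will be assumed to be smokers". The SAP states no missing-data rule for the dose, resolution or per-protocol analyses, no method for handling self-selection, and no caution on interpretation.

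For problem resolution, Protocol 1.13 gives the source: "Follow-up surveys also will assess changes in unmet basic needs", and the same surveys ask whether each problem behind the 2-1-1 call has been resolved. They also record smoking status.

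**The concern.** A sensitivity analysis asks whether the randomized answer survives a change in assumptions. A comparison of people who took many calls with people who took few asks something else, because the participants sorted themselves into those groups. The documents show three routes by which the sorting can be tied to quitting.

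- **Reachability.** All contact is by telephone (Protocol 1.3), and coaches make up to five attempts per session (Protocol 1.13). A person who is hard to reach for coaching may also be hard to reach for the survey, and is then scored a smoker.
- **Reverse causation.** Protocol 1.13 says calls are adjusted to the participant's quit success.
- **Confounding.** Protocol 1.5 says quitline users given nicotine replacement complete more sessions. It also cites abstinence of 12% with multi-session counselling and up to 35% when nicotine replacement is added. Protocol 1.21 makes free nicotine replacement depend on insurance status.

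The stake is interpretation. If the randomized comparison is null, a finding that more contact goes with more quitting, reported under a robustness heading, could be read as support for the intervention.

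**Working it through.** **Reproducing the plan's figures.** SAP 1.23 expects at least 60% follow-up of 2000: 2000 × 0.60 = 1200, so up to 800 (40%) would be scored as smokers. Protocol 1.13 expects fewer than 14% of respondents to be abstinent and off nicotine replacement: 1200 × 0.14 = 168. Both match. For scale, the planning odds ratio of 1.8 at a 10% total quit rate means about 7.4% versus 12.6%, a difference of 5.2 points.

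**Scoring artefact for calls and contacts.** Suppose the intervention does nothing and respondents quit at the same rate q at every dose. If missing counts as smoking, then

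counted quit rate = follow-up × q.

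Take q = 10% (assumed) and let follow-up differ between low and high dose around the planned 60% (also assumed, since the documents give no follow-up by dose). Significance is from a two-proportion test at two-sided 0.05. The SAP states no alpha; this is inferred from its 95% confidence intervals.

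| Follow-up, low / high dose | Counted quit rates | OR | Significant, 500 vs 500 |
|---|---|---|---|
| 60% / 60% | 6.0% / 6.0% | 1.0 | about 5% |
| 55% / 65% | 5.5% / 6.5% | about 1.2 | about 10% |
| 50% / 70% | 5.0% / 7.0% | 1.43 | about 27% |
| 40% / 80% | 4.0% / 8.0% | 2.1 | about 76% |

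Example, last row: (0.08/0.92) ÷ (0.04/0.96) = 0.0870 ÷ 0.0417 = 2.09.

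The 500 is borrowed from the arm size for illustration; no dose-group size is planned. With five equal groups of 400 (0 to 4 calls), the two extreme groups give about 22% for the third row and 66% for the fourth. A trend test over all 2000 returns about 27% and 76%. With q = 14%, the trend test gives about 36% and 89%.

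**Does complete case remove it?** This was checked by simulation: 1000 replicates of 2000 participants, no effect of dose or arm, and latent engagement driving dose and, in turn, follow-up or quitting.

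- *Follow-up differs, quitting does not* (46% followed up at the lowest dose, 73% at the highest): missing = smoker gives OR 1.67, significant in 55%. Complete case gives OR 1.01, significant in 5%.
- *Quitting differs through self-selection, follow-up flat at 60%*: respondent quit rates of 11.2% and 16.9% become 6.7% and 10.1% once missing counts as smoking. The OR is 1.61 among respondents and 1.56 with missing = smoker. Across two strengths of self-selection, the respondent OR is 1.6 to 2.2, significant in 49% to 90%.
- *Neither linked to dose*: OR 0.99, significant in about 4%.

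So restricting to respondents removes the follow-up artefact and leaves self-selection in place.

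**Where the scoring artefact does not reach.** Six-month problem resolution comes from the same survey as the outcome, so a participant scored as a smoker for non-response has no resolution value and cannot contribute to that gradient. Three-month resolution could be affected, for participants reached at 3 months and lost by 6. A per-protocol comparison between arms has no dose axis: with the same adherence selection in both arms, the simulation found 4% to 6% significant. Bias there needs exclusions that differ by arm.

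**The case against.** The strongest reply is that the SAP never says missing = smoker applies to the dose analyses. The rule sits with the ITT group quit rates, and a complete-case comparison is planned. That stands as far as it goes: carrying the rule over is an inference, made because the SAP gives these analyses no rule of their own, and the complete-case comparison is not linked to dose. Protocol 1.12 also provides for collateral contacts, which may weaken the link between being missed for coaching and being missed for the survey.

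A reader might infer that the plan is bound to produce a false dose-response. The documents do not support that. They report neither follow-up nor quitting by dose, and with no association there is no artefact. Nor do they support extending the scoring mechanism to per-protocol comparisons or to six-month problem resolution. Nothing in the plan says that dose results will be presented as evidence of efficacy.

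The complier estimate can also be challenged. Its numerator is the ITT difference, itself scored with missing = smoker. If navigator contact keeps people reachable, that scoring effect enters the numerator and is enlarged by the division. This is why both scorings should be shown. It offers no simple ratio for the quitline factor, because both quitline types deliver calls.

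**Conclusion.** The point holds as a matter of labelling and interpretation. Calls, contacts, per-protocol status and problem resolution are post-randomization and partly self-selected, so agreement or disagreement with the ITT result says little about robustness. For calls and contacts, a null intervention can show an odds ratio from 1.0 to about 2.1 over the assumed follow-up range, which spans the planning value of 1.8. This rests on missing = smoker being carried into those analyses and on follow-up rising with dose; neither is stated. For problem resolution the risk is confounding or reverse causation. For per-protocol it is an undefined population whose exclusions may differ by arm.

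A reader might infer that the trial's main conclusion is compromised. It is not: the primary randomized comparison does not use any of these variables. The point is a low-cost improvement to the plan.

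**What to change.** 1. Move the dose and problem-resolution analyses out of the robustness set. Label them descriptive, avoid causal wording, state the missing-data rule for each, and report them among 6-month respondents. Say in the text that this removes the follow-up artefact but not self-selection.
2. For the navigator factor, report a complier average causal effect in place of, or beside, per-protocol: the ITT difference in quit rates divided by the proportion of navigator-arm participants with at least one navigator contact. The non-navigator arms have no access to a navigator (Protocol 1.7). Give it under both missing = smoker and complete case, and state the assumption that assignment acts only through contact.
3. If per-protocol is kept, as it may be for the quitline factor, define its population by the same rule in every arm.
4. Reconcile the call count before fixing a dose scale: Protocol 1.13 describes one call before and four after the quit date, and also up to four sessions.

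The cost is SAP wording and a little more analysis. The complier estimate has a wider interval than the ITT difference, by roughly 1 divided by the proportion contacted.
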